The results of this study may help synthesize complex intraoperative clinical information and unveil novel therapeutic strategies. Derived from data from the QEII Hospitals, the results would be directly applicable to the care of Nova Scotians. The models may lead to the creation of objective risk stratification scores calculated at the end of surgery, to identify high risk patients for increased postoperative follow-up and monitoring. Moreover, if models created using machine learning perform well, machine learning may be used more frequently to reveal the patterns within complex, large perioperative datasets. Hemodynamics are potentially modifiable risk factors. Future research includes prospective studies on whether targeted hemodynamic goals, increased postoperative follow-up of high-risk patients, and real-time machine learning precision medicine could improve outcomes after surgeries.

Specific aims

1. To use machine learning techniques to investigate systematically intraoperative hemodynamic predictors of postoperative 30-day all-cause mortality (primary outcome) and major in-hospital morbidity. Hemodynamic predictors to be studied are blood pressure, heart rate, oxygen saturation, end-tidal carbon dioxide, and medications to adjust blood pressure. Please see “Outcomes” section below for full list of secondary outcomes.
2. To evaluate performance of machine learning models created and compare the performance of the best model to the Surgical Apgar Score.

Hypothesis

Controlling for other predictors, the durations of mean arterial pressure (MAP) <65mmHg, heart rate <60 or >100 beats per minute (BPM), hemodynamic medications use, oxygen saturation (SpO₂) <88%, and end-tidal carbon dioxide (EtCO₂) <30 or >45 will be associated with postoperative 30-day all-cause mortality (primary hypothesis) and 30-day major in-hospital morbidity (secondary hypothesis). Note that blood pressure, heart rate, vasopressors and

inotropic medications, oxygen saturation, and end-tidal are considered key indicators of hemodynamics. We have chosen conventional ranges commonly used in practice, and will perform sensitivity analysis of different definitions of each hemodynamic variable.

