At the time of surgery, anesthesiologists document the timing of key clinic information (induction, intubation, start and end of surgery, emergence, extubation, and exit of the operating room), medications and fluids administered, estimated blood loss, and type of anesthesia into the intraoperative record. Hemodynamic factors are automatically recorded into the database every minute. The following intraoperative hemodynamic factors will be included in model building:

Table 1. Exposures

Blood pressure	
Since there is no universal definition of low blood pressure under anesthesia, we will use several different variables to determine the most significant exposure by threshold and duration. Both Systolic Blood Pressure (SBP) and Mean arterial pressure (MAP) have been used in blood pressure research (12). In a recent study (26), different blood pressure modeling techniques on the same dataset led to different conclusions on the impact of hypotension on postoperative myocardial infarction and kidney injury. Methods with the largest odds ratios were absolute maximum decrease in MAP and mean episode area under threshold. However, since the area under threshold is less interpretable and difficult to calculate in everyday clinical practice, the duration under threshold will be used.
 
SBP
 
1. Maximum change from preoperative SBP, in a) absolute change (mmHg), and b) relative change (%) (emergency and elective cases analyzed separately due to the lack of preoperative blood pressure in the emergency group)2. Cumulative duration (minutes) $\geq 20\%$ below preoperative SBP3. Longest single episode (minutes) below a) 80, b) 90, and c) 100 mmHg4. Cumulative duration (minutes) below a) 80, b) 90, and c) 100 mmHg 
MAP
 
1. Maximum change from preoperative MAP, in a) absolute change (mmHg), and b) relative change (%) (emergency and elective cases analyzed separately due to the lack of preoperative blood pressure in the emergency group. Note that since the HSM database only contains SBP and DBP, not MAP, MAP will be calculated using $MAP = 1/3*SBP + 2/3*DBP$)2. Cumulative duration (minutes) $\geq 20\%$ below preoperative MAP3. Longest single episode (minutes) below a) 60, b) 65, c) 70, and d) 80mmHg4. Cumulative duration (minutes) below a) 60, b) 65, c) 70, and d) 80mmHg
-----------------------	---

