Heart rate	Since both fast and slow heart rate may be harmful and there is no universal definition of abnormal heart rate under anesthesia, we will model using a variety of methods. 
 1. Maximum change (BPM) from preoperative heart rate (positive and negative) 2. Relative change (%) from preoperative heart rate (positive and negative) 3. Maximum pulse variation (maximum heart rate minus minimum heart rate) 4. Longest single episode (minutes) a) below 60, and b) above 100BPM 5. Cumulative duration (minutes) a) below 60, and b) above 100BPM
Use of hemodynamic medications (i.e. special medications for blood pressure)	
 1. Vasopressor/inotrope use (yes vs. no): phenylephrine, norepinephrine, epinephrine, vasopressin, dobutamine, or milrinone 2. Infusion of any vasopressor/inotropes above (yes vs. no) (identified by unit of weight over time) 3. Phenylephrine/ephedrine bolus (yes vs. no) (identified by unit of weight only) 4. Vasodilator use (yes vs. no): labetalol, esmolol, nitroglycerin, nitroprusside 5. Infusion of any vasodilator above (yes vs. no) (identified by unit of weight over time)
Oxygen saturation by pulse oximetry: SpO₂	
 1. Longest single episode (minutes) below a) 88, and b) 90% 2. Cumulative duration (minutes) below a) 88, and b) 90%
End-tidal (i.e. exhaled) Carbon dioxide: EtCO₂	
 1. Longest single episode (minutes) a) below 30, and b) above 45mmHg 2. Cumulative duration (minutes) a) below 30, and b) above 45mmHg

II. Outcomes

Primary: 30-day all-cause postoperative mortality (binary)

Secondary:

1. Major 30-day in-hospital morbidity, both in terms of the individual category (yes/no), and an overall composite (i.e. yes for any of the 6 categories vs. no). We have included major morbidity outcomes where increased monitoring would be beneficial, using International Statistical Classification of Diseases (ICD) 10 codes and based on published protocol on patient safety indicators (27).
 1. Cardiac: composite of acute myocardial infarction, cardiac arrest, ventricular tachycardia, congestive heart failure, pulmonary edema, complete heart block, shock excluding septic shock
 2. Respiratory: composite of pneumonia, pulmonary embolism, acute respiratory failure, respiratory arrest, Mechanical Ventilation \geq 96 hours
 3. Acute Kidney Injury
 4. Cerebrovascular: composite of strokes and transient ischemic attacks

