New variables will be created through calculation or dichotomization, as described in the variables section above and Appendix 1. Patients with age >120 or ≤ 45 will be flagged for further investigation of data validity and potential removal. Artifact removal from hemodynamic variables will be performed by the Innovian Database Manager in SQL, prior to creation of exposure variables (Table 1) and data linkage. Input of hemodynamic variables of interest (blood pressure, heart rate, EtCO₂, and SpO₂) as well as BIS and end tidal volatile from intraoperative monitors were automatically recorded every 15 seconds into Innovian. Continuous values were captured every 15 seconds as medians of 8 values captured every 2 seconds, while discrete values (e.g. NIBP) were captured as is at the moment. The maximum incidence of artifact was found to be 0.1% for heart rate, 0.4% for SpO₂, 2.9% for noninvasive blood pressure, and 15% for invasive blood pressure in a previous study (39), and this is likely an overestimate due to the strict definition of artifacts. A systematic review and cohort study showed that while a variety of different artefact algorithms affected the defined incidence of intraoperative hypotension, it did not significantly affect the model between hypotension and outcome (40). Importantly, duration-based hypotension definitions were less affected by artefact filtering algorithms than depth thresholds (40).

To reduce artifacts outside of anesthesia time (e.g. arterial line is plugged in prior to patient arrival), the variables below will only be taken during a defined “Surgery Duration”. This Duration starts at the first valid recorded SpO₂ (that is subsequently valid for 1 minute), and ends after the last valid SpO₂ (that has been valid for 1 minute).

- **Blood pressure**

1. **Step 1, removal of individual artifacts:** Note that non-invasive (NIBP) and invasive blood pressure values (IABP) will be treated separately. Potential artifacts will be removed (changed to missing data) in the following order:

1. Missing any of SBP, DBP, or MAP, or where any of SBP, DBP, and MAP are equal to each other

2. Apply 3 different artifact algorithms simultaneously to identify artifacts:

- Multi-Centre Perioperative Outcomes Group (MPOG) algorithm
- For IABP only: MAP value greater than 50% from the values before and after will be deleted, as previously described by Sun et al (41).

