 2. Heart rate > 170 or < 30 BPM will be removed. To reduce the influence from outlier artifacts (e.g. temporary disconnection or adjustment of a monitor), single episodes of deviation in any variable greater than 50% above or below the preceding value will be flagged. If the flagged heart rate from the pulse oximeter and ECG (and/or arterial line) differ by >10 , the heart rate will be removed as artifact.
2. Clarification about “Baseline” heart rate: similar to BP above, the HSM and first Innovian HR will be modeled separately during analysis, i.e. each patient will have two “baseline” HR. All patients will have the variable of a first Innovian HR (after artifact clean up). Only some patients will have HSM HR (i.e. preoperative clinic or in the preadmission area). If a patient does not have a HSM HR, the variable value will be coded as missing (not zero).

- **EtCO₂** will only be analyzed in cases involving general anesthesia. Values > 120 or < 5 mmHg will be removed as artifact.
- **SpO₂** > 100% or < 50% will be removed as artifact.
- **Temperature** < 30 or > 43 degrees Celsius will be removed as artifact.
- **End tidal volatile concentrations** (including nitrous oxide) will be converted to summed age-adjusted MAC (36). The total age-adjusted MAC < 0.2 and > 2.5, at each 15 second interval, will be removed as artifact prior to calculation of the time-weighted average (15 second time intervals).

For each automatically recorded variable from Innovian, at least 3 cases will be reviewed to ensure correct artifact labeling. We will quantify the percentages of artifacts flagged and removed per case for each variable monitored.

Artifact Removal Sub-study: Derivation of a machine learning algorithm for artifact removal for invasive blood pressure data

Rationale

While putting together the Innovian dataset for our study, we found that existing artifact (noise) removal algorithm has limitations at removing invasive arterial blood pressure (IABP) artifacts. Current algorithms are based on clinician-generated rules (40). We plan to use machine learning algorithms to improve artifact detection.

Objective

Our goal is to derive an artifact removal algorithm for IABP using machine learning of hemodynamic data.

Methodology

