Innovian	SpO₂: Oxygen saturation by pulse oximetry [Derived by Innovian as multiple variables – see right]	Patient	Jan 1, 2013 to Dec 1, 2017	
Exposure variable to be included into modeling. The following variables will be derived by Innovian:
 
3. Longest single episode (minutes) below a) 88, and b) 90%
 
4. Cumulative duration (minutes) below a) 88, and b) 90%

Innovian	EtCO₂: End-tidal (i.e. exhaled) [Derived by Innovian as multiple variables – see right]	Patient	Jan 1, 2013 to Dec 1, 2017	
Exposure variable to be included into modeling. The following variables will be derived by Innovian:
 
1. Longest single episode (minutes) a) <35, and b) >45
 
2. Cumulative duration (minutes) below a) <35, and b) >45

HSM	Duration of surgery	Patient	Jan 1, 2013 to Dec 1, 2017	As this may affect outcomes, it will be included as a covariate
Innovian	Type of anesthesia	Patient	Jan 1, 2013 to Dec 1, 2017	Categorical variable: general, neuraxial, peripheral nerve block, and/or managed anesthesia care [i.e.

				
sedation] – multiple concurrent possible). As this may affect outcomes, it will be included as a covariate.
 
Innovian will be used instead of the CIHI ANATYP (Anaesthetic Type), since anesthetic type is a mandatory field in Innovian and will allow for multiple concurrent anesthetic types.

Innovian	Average MAC-adjusted: Minimal Alveolar Concentration adjusted by age [Derived by Innovian]	Patient	Jan 1, 2013 to Dec 1, 2017	Age-adjusted MAC will be calculated by Innovian from the end-tidal % of all inspired volatiles according to published protocol (36). The MAC, available every 15 seconds will be averaged (i.e. time-averaged MAC). The averaged MAC will be included as a covariate.
Innovian	BIS : Bi-spectral Index [Derived by Innovian]	Patient	Jan 1, 2013 to Dec 1, 2017	Duration in minutes for BIS <46. As deep anesthesia (low BIS) may affect outcomes (50), it will be included as a covariate.
Innovian	Laparoscopy-booked [Derived by Innovian]	Patient	Jan 1, 2013 to Dec 1, 2017	Binary variable (yes/no), as defined by “laparoscope” or “laparoscopic” in procedure name.
DAD	Laparoscopy converted to open flag STATUS[1-n] [Flag by HDNS]	Patient	Jan 1, 2013 to Dec 1, 2017	
Flag: STATUS[1-n] = C “Converted from endoscopic to open”
 
Since Innovian procedure names are usually from OR booking, procedures where laparoscopy was converted to open would be included in the laparoscopy (booked) variable.

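### The only time limit on EtCO₂ is set by pulse oximetry, so low readings before the airway is in place or after it is removed can be counted as low-EtCO₂ exposure

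*Combined protocol and SAP*

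**What the plan says.** - **Window.** Data processing and artifact removal sets one window for all monitored variables: "the variables below will only be taken during a defined" Surgery Duration. Its purpose is given as "To reduce artifacts outside of anesthesia time (e.g. arterial line is plugged in prior to patient arrival"). It is defined thus: "This Duration starts at the first valid recorded SpO₂ (that is subsequently valid for 1 minute), and ends after the last valid SpO₂".
- **EtCO₂ rules.** The EtCO₂ bullet in the same section says that this variable "will only be analyzed in cases involving general anesthesia. Values > 120 or < 5 mmHg will be removed as artifact". It gives no start or end time.
- **Exposure.** Table 1 derives the longest single episode and also "Cumulative duration (minutes) a) below 30, and b) above 45mmHg". For the same variable, Appendix 1 has "Cumulative duration (minutes) below a) <35, and b) >45".
- **Role.** The Hypothesis section lists durations of EtCO₂ below 30 or above 45 among the exposures that "will be associated with postoperative 30-day all-cause mortality (primary hypothesis").
- **Times on file.** Variables, I. Main Predictors says that anesthesiologists document the timing of "induction, intubation, start and end of surgery, emergence, extubation, and exit of the operating room".

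**The concern.** Valid pulse oximetry shows that a probe is on the patient. It does not show that an airway is in place or that exhaled gas is being sampled reliably. The baseline blood pressure clarification confirms that recorded time can include the period before induction: it takes the first reading as baseline because the second may already follow induction. The window can therefore contain minutes outside airway control in a general-anesthesia case, and nothing in the EtCO₂ rules removes a low reading from those minutes.

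At stake is the meaning of a primary-hypothesis exposure. If such readings are recorded, low-EtCO₂ time becomes a mixture of low values under a controlled airway and low values from outside that period. The second part could vary with airway difficulty or the speed of emergence, which may or may not be related to risk. The exposure is derived on the Innovian side before linkage and reaches the analysts as totals in minutes. Once it is derived, the two parts cannot be separated without a new extraction.

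**Working it through.** The plan gives no figure for EtCO₂ minutes outside airway control, so there is nothing to reproduce. The check is on the rules, followed by an illustration under stated assumptions.

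**Step 1. Follow one reading through the rules.** Take 20 mmHg recorded inside the SpO₂ window but before the airway is in place, in a general-anesthesia case.

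| Stated rule | Effect on this reading |
|---|---|
| Surgery Duration (first to last valid SpO₂) | Kept: inside the window |
| General-anesthesia restriction | Kept: selects cases, not minutes |
| Removal below 5 or above 120 mmHg | Kept: 5 < 20 < 120 |
| Flag for single deviations over 50% | At most flagged; a removal criterion is given only for heart rate |
| Review of at least 3 cases per variable | Checks labelling; no rule labels this reading |
| Threshold below 30 (Table 1) or below 35 (Appendix 1) | Counted under either |

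The reading adds to the cumulative duration. It affects the longest episode only where it belongs to the longest run.

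**Step 2. Compare with other variables.** Invasive pressure has an added rule for readings before arterial line insertion (minimum first MAP and SBP). Volatile agent records with summed age-adjusted MAC below 0.2 are dropped. EtCO₂ has no comparable rule tied to when its measurement is meaningful.

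**Step 3. Illustrate the added minutes (assumed inputs, not from the documents).**

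Added minutes = (minutes in the window without an airway in place) × (share of those records from 5 mmHg to below the threshold).

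| Assumed minutes | Share 10% | Share 100% |
|---|---|---|
| 4 | 4 × 0.1 = 0.4 | 4 |
| 8 | 8 × 0.1 = 0.8 | 8 |
| 15 | 15 × 0.1 = 1.5 | 15 |

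If no such readings are recorded, or all are below 5 mmHg, the result is 0.

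**Step 4. Illustrate the effect on a linear slope.** If the added minutes are independent of true low-EtCO₂ minutes, the slope is multiplied by SD_true² / (SD_true² + SD_added²).

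| Assumed SD_true (min) | Assumed SD_added (min) | Factor |
|---|---|---|
| 5 | 5 | 25 / (25 + 25) = 0.50 |
| 5 | 3 | 25 / (25 + 9) = 0.74 |
| 15 | 3 | 225 / (225 + 9) = 0.96 |
| 30 | 1 | 900 / (900 + 1) = 0.999 |
| any | 0 (same offset in every patient) | 1 |

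The last row matters: a constant offset leaves the slope unchanged. It would only shift the minutes axis on which the planned splines are read. If the added minutes are related to risk, the formula does not apply and the direction of bias cannot be stated.

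**The case against.** The case for leaving the window as it is has four parts.

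1. **No evidence of occurrence.** No section says that CO₂ is recorded at a mask before induction or after extubation, or that such readings fall at 5 mmHg or above. This stands. A reader might infer that every general-anesthesia case carries several false minutes, or that exposure is overstated by some percentage. For example, 2 to 10 false minutes on 5 true ones would give (5 + 2)/5 = 1.4 to (5 + 10)/5 = 3.0, an overstatement of 40% to 200%. Both inputs would be invented, and the documents support neither statement.
2. **An inflated total is not a biased association.** This also stands, as the last row of Step 4 shows. Only between-patient variation matters. The longest-episode measure is untouched when a true episode is longer than, and separate from, the run outside airway control.
3. **Other safeguards exist.** The 50% flag, the three-case review and the sensitivity analyses of hemodynamic definitions are real. None of them removes the readings, and no alternative time window is specified among the sensitivity analyses.
4. **The SpO₂ window uses automatic data.** Event times are manual entries, and the Data quality paragraph accepts that anesthesiologist entries cannot be checked retrospectively. This is a genuine cost of the change. It is a reason to keep the SpO₂ window as a sensitivity analysis and to state fallbacks. It is not a reason to leave the gap, because the plan already relies on manual entries for its medication exposures.

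**Conclusion.** The gap in the rules is real and rests on the text alone. The single window does not fully serve its own aim for EtCO₂, and low readings from outside airway control can enter a primary-hypothesis exposure. The change should be made before the exposure is derived.

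The consequence is unquantified. The 0.4 to 15 added minutes and the slope factors of 0.50 to 0.999 depend entirely on assumed inputs and show only that the effect could be negligible or material. It would be wrong to conclude that the plan creates a spurious EtCO₂–mortality association, that it necessarily weakens a true one, or that all general-anesthesia cases are affected. The point concerns low EtCO₂ only and does not question the window for the other variables.

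A related inconsistency bears on size: the low threshold is 30 in the Hypothesis and Table 1 but 35 in Appendix 1. The higher value would admit at least as many of these readings. The passages must be reconciled.

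**What to change.** For EtCO₂ only, replace the window as follows, before derivation:

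- **Start:** recorded intubation time, or induction time if there is no intubation entry.
- **End:** recorded extubation time, or emergence time if there is no extubation entry.
- **Patient left the room still intubated:** end at the last valid SpO₂, and state how these cases are identified. Do not fall back to the end of surgery, which would selectively shorten measured exposure in these patients.
- **Entries simply missing:** use one pre-stated fallback and report how often it is used.

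Keep the SpO₂ window for the other variables. Report the EtCO₂ results under the SpO₂ window as a sensitivity analysis; the difference between the two versions measures the size of the problem. State one low threshold throughout.

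The cost is a short paragraph in the plan, a few conditions in the extraction code and a second set of EtCO₂ variables. The main downside is reliance on manual event times that cannot be validated afterwards. A smaller one is that, without an intubation entry, starting at induction still keeps any mask ventilation before another airway device is placed.

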- The following blood pressure artifact removal rules as described by Salmasi et al (41) will also be applied: “SBP less than or equal to DBP + 5 mmHg”, and “abrupt changes defined by SBP change greater than or equal to 80 mmHg within 1 min in either direction or abrupt SBP changes greater than or equal to 40 mmHg within 2 min in both directions.”

3. To remove artifacts prior to arterial line insertion, for IABP data only, the first MAP readings must be >40 , and the first SBP reading must be >60 .
4. For each BP measurement, if any of SBP or MAP has been labelled as an artifact, then remove the entire measurement.
5. If an entire case has been identified as null after artifact removal (i.e. no valid BP for the entire case), the entire case and studyID will be deleted.

2. Step 2. Concatenation. The final blood pressure will be taken from IABP or NIBP, whichever is available after artifact removal. If both non-invasive (NIBP) and invasive blood pressure values (IABP) are available for the same 15 second interval, the higher reading will be taken. Otherwise, the only blood pressure that is valid will be used.

3. Clarification re. “Baseline” blood pressure: The HSM and first Innovian BP will be modeled separately during analysis, i.e. each patient will have two “baseline” measurements, coded by the variables “MAP_first_Innovian” and “MAP_preop_HSM”.

1. All patients will have the variable of a first Innovian BP (after artifact clean up). The first Innovian BP is used since the second BP may be postinduction. This has the limitation that the the first intraoperative BP may not reflect the true baseline (42); however, practically this would be the blood pressure that would be available in similar clinical situations.
2. Only some patients will have HSM BP (i.e. at preoperative clinic or in the preadmission area). Since the HSM does not contain MAP, MAP will be calculated using $MAP = (2/3 DBP) + (1/3 SBP)$.
 - If a patient does not have a HSM BP, the variable value will be coded as missing (not zero).

- **Heart rate**

1. Artifact removal:
 1. The heart rate will be collected from the pulse oximeter instead of ECG, to reduce risk of electric cautery artifact and non-transmitted conduction.

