Innovian	First systolic blood pressure (SBP) [Derived by Innovian]	Patient	Jan 1, 2013 to Dec 1, 2017	Emergency and elective cases will be analyzed separately for the variables containing relative SBP changes, recognizing the lack of preoperative blood pressure in the emergency group. For patients with BP recorded on HSM (i.e. preoperative clinic or in the preadmission area), the lowest of the HSM or first Innovian BP will be used as baseline. For emergency surgery patients without previously recorded blood pressure, the first Innovian BP will be used (since the second BP may be postinduction), with the limitation that this may not reflect the true baseline (42); however, practically this would be the blood pressure that would be available in similar clinical situations.
HSM	Preoperative mean arterial pressure (MAP) [Derived by Innovian]	Patient	Jan 1, 2013 to Dec 1, 2017	Since the HSM database only contains SBP and DBP, not MAP, MAP will be calculated using $MAP = 1/3*SBP + 2/3*DBP$
Innovian	First mean arterial pressure (MAP) [Derived by Innovian]	Patient	Jan 1, 2013 to Dec 1, 2017	Emergency and elective cases will be analyzed separately for the variables containing relative MAP changes, recognizing the lack of preoperative blood pressure in the emergency group. For patients with BP recorded on HSM (i.e. preoperative clinic or in the preadmission area), the lowest of the HSM or first Innovian BP will be used as baseline. For emergency surgery patients without previously recorded blood pressure, the first Innovian BP will be used (since the second BP may be postinduction), with the limitation that this may not

				reflect the true baseline (42); however, practically this would be the blood pressure that would be available in similar clinical situations.
HSM	Preoperative heart rate	Patient	Jan 1, 2013 to Dec 1, 2017	
As this may affect the level of harm from the intraoperative heart rate, it will be used in the calculation of change in heart rate (absolute and %)
 
HSM contains heart rate of elective surgery patients at the anesthetic clinic and prior to entering the operating room, while Innovian contains the initial heart rate of all patients in the operative room. The lowest heart rate from either Innovian or HSM will be used.

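### If the first cuff reading is deleted as artifact, a later and possibly post-induction reading silently becomes the operating-room blood pressure baseline

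*Combined protocol and SAP*

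**What the plan says.** All references are to the combined protocol and SAP.

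- **Baseline rule.** Data processing and artifact removal, Blood pressure, item 3, says that every patient will have a "first Innovian BP (after artifact clean up). The first Innovian BP is used since the second BP may be postinduction". Appendix 1 repeats this for emergency patients with no earlier pressure: "the first Innovian BP will be used (since the second BP may be postinduction").
- **Order of work.** Artifacts are removed "prior to creation of exposure variables (Table 1) and data linkage".
- **When a case is dropped.** Only in this situation: "If an entire case has been identified as null after artifact removal (i.e. no valid BP for the entire case"). Losing the first reading alone does not drop the case.
- **Window.** "This Duration starts at the first valid recorded SpO₂ (that is subsequently valid for 1 minute"). Induction plays no part in it.
- **Induction time.** Under Main Predictors, "anesthesiologists document the timing of key clinic information (induction, intubation, start and end of surgery, emergence, extubation, and exit of the operating room").
- **Second baseline.** Item 3 also models an HSM pressure separately. Only some patients have one, and an absent value is coded as missing. For patients who have an HSM reading, Appendix 1 instead uses the lower of the HSM and first Innovian pressures.

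**The concern.** The reason for choosing the first reading is to stay ahead of induction, but the operative rule is the first reading that survives cleaning. When the first cuff reading is deleted, the rule selects the kind of reading its rationale was meant to avoid. It does so without a flag, because every retained patient is declared to have a value.

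The exposures at stake in Table 1 are the maximum absolute and relative change from preoperative SBP and MAP, and the cumulative minutes at least 20% below preoperative SBP and MAP. A falsely low baseline lowers the 20% threshold and shrinks the measured fall. Table 1 sets these definitions beside absolute thresholds to see which matters most, so an error confined to the relative ones makes that comparison slightly uneven. The stated limitation, that the first intraoperative pressure may not be the true baseline, does not cover substitution by a later reading.

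**Working it through.** The plan gives no figure for displaced baselines, so there is none to reproduce.

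**1. Does the rule permit substitution?** Cleaning precedes derivation, every retained patient has a value, and a case is dropped only if no valid pressure remains. So a deleted first reading is replaced and is not set to missing. No section adds a condition relative to induction.

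**2. Reach.** Inputs from the plan: about 35,000 patients, 24,000 in derivation, 1.7% mortality, and a cited maximum artifact rate for non-invasive pressure of 2.9%. The plan calls that rate likely an overestimate. Applying it to first readings is an assumption, as is the 1% alternative.

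- 35,000 × 0.029 = 1,015
- 35,000 × 0.01 = 350
- Derivation set: 24,000 × 0.029 = 696, with 696 × 0.017 ≈ 12 of the 408 expected deaths

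**3. Effect in one affected patient** (assumed pressures). With MAP 95 before induction and 72 after, the 20% threshold moves from 0.8 × 95 = 76 to 0.8 × 72 = 57.6 mmHg.

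**4. Average over affected patients** (all inputs assumed). True baseline B ~ N(95, 12). Post-induction mean M = B × F, with F ~ N(0.76, 0.08). Within-case SD 8 mmHg, 120 minutes, 200,000 simulated patients.

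Minutes = 120 × Φ((0.8 × baseline − M)/8), where the baseline is either B or one draw from N(M, 8).

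- True baseline: 76.2 minutes
- Post-induction baseline: 10.2 minutes, correlation with the true count 0.16
- Mean falls at induction of 10%, 15% and 20% in place of 24%: 24 to 6, 40 to 8 and 60 to 9 minutes, correlations 0.17 to 0.18

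**5. Cohort average.** The relative loss in an affected patient is 1 − 10.2/76.2 = 0.866.

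- 2.9% affected, every replacement post-induction: 0.029 × 0.866 = 2.5% of mean minutes; correlation with the true exposure about 0.93
- 1% affected: 0.01 × 0.866 = 0.9%; correlation about 0.97

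**6. Cross-check with a simpler model** (assumed intraoperative MAP ~ N(78, 12), 120 minutes, true baseline 95).

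| Baseline used | 20% threshold (mmHg) | Minutes below |
|---|---|---|
| 95 (true) | 76.0 | 52.1 |
| 10% lower | 68.4 | 25.4 |
| 20% lower | 60.8 | 9.1 |
| 30% lower | 53.2 | 2.3 |
| 10% higher | 83.6 | 81.6 |

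With 2.9% of patients affected and each baseline 20% too low, the cohort mean falls by 0.029 × (1 − 9.1/52.1) = 2.4%. If only a quarter of those replacements are that low, it falls by 0.6%. The last row shows that a higher replacement reverses the sign.

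**The case against.** The strongest objection is that the problem is rare and bounded, and most of that stands.

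- **Direction.** A reader might infer that the error always under-counts. The plan says only that the second reading may be post-induction. A second pre-induction reading does little harm, and a higher one over-counts.
- **Missed hypotension.** A reader might infer that severe post-induction hypotension goes unrecorded. That could be true only of the baseline-relative variables. Table 1 also scores minutes below MAP 60, 65, 70 and 80 and SBP 80, 90 and 100, and the primary hypothesis uses MAP below 65. None of these needs a baseline.
- **Heart rate.** The wording is parallel: "All patients will have the variable of a first Innovian HR (after artifact clean up"). But heart rate is stored every 15 seconds with a cited maximum artifact rate of 0.1%, so an isolated deletion moves that baseline by seconds. The effect is negligible.
- **Invasive pressure.** It too is stored every 15 seconds and is cleaned separately before merging. Deleting an arterial start-up value does not displace a valid earlier cuff reading.
- **Window.** A reader might infer that the first minute of oximetry is excluded. The window opens at the first valid value, so that minute is inside. Readings before any valid oximetry are excluded on purpose; the documents give no count of them, and they are not in the reach above.
- **HSM baseline.** As item 3 is written, it is modelled separately and is unaffected. That protection fails if the Appendix 1 rule is applied, because the lower of the two pressures would let a falsely low Innovian value override a sound HSM one.

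The objection does not remove the inconsistency. The planned checks, artifact percentages per case and review of at least 3 cases per variable, would not show how often the baseline reading was the one removed.

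**Conclusion.** The concern holds as a limited defect. The baseline rule can select a reading that its own rationale rejects, and nothing in the documents prevents or records this. Reach is at most about 1,015 of 35,000 if the 2.9% maximum applies to first readings, and about 350 at an assumed 1%. Under-counting also requires the replacement to be post-induction and lower. In such a patient the loss can be large (about 76 to 10 minutes under the assumed inputs), but the cohort mean moves by roughly 1% to 2.5% even if every replacement is post-induction. The consequence falls mainly on patients with no HSM pressure, many of them emergency cases, who have no other baseline. The documents do not support reading this as a threat to the primary-hypothesis blood pressure exposure. The case for acting is that the correction is cheap and restores the plan's stated intent.

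**What to change.** 1. Where an induction time is recorded, define the first Innovian SBP and MAP as the first valid reading inside the existing oximetry window and time-stamped before induction. If none survives, code that baseline as missing, as is already done for HSM.
2. Where no induction time is recorded, keep the current rule, but flag cases in which the first recorded reading was removed.
3. Report how many baselines are missing and how many are not the first recorded reading, separately for emergency and elective cases.
4. Amend the statement that all patients will have a first Innovian pressure, and reconcile item 3 (two baselines modelled separately) with the Appendix 1 blood pressure rows (the lower of the two).

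The oximetry window should stay in force for this variable, because it exists to keep out artifacts from before the patient is monitored.

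**Cost.** One time-stamp condition and one flag in the Innovian SQL. A small share of patients lose the Innovian baseline. If the Missing data rule of no processing below 5% is applied to them, they may drop out of any model that includes a baseline-relative exposure. The condition also relies on clinician-entered induction times, and the Data quality paragraph says physician entries cannot be validated retrospectively.
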